9.6. Physical Examination

A complete physical examination of body systems (excluding breast and genitourinary examinations) according to standard of care and a neurological examination (including cranial nerves, muscle strength and tone, reflexes, coordination, sensory function, and gait, all as applicable for the patient's age) will be performed at Screening, Day 1, and Weeks 2, 4, 5, 6, 9, and 12.

Frequencies and percentages of physical examination interpretation results (normal, abnormal clinically significant, and abnormal not clinically significant) will be summarized by treatment group within treatment period and study visit for each body system on patients in the Safety Set.

In addition, physical examination results will be summarized in listing.

9.7. Local Tolerability

Local tolerability data will be collected separately from AEs at Day 1 and Weeks 2, 4, 5, 6, and 9. Data will be collected on the nature of any reaction (including spontaneous pain, pain on palpitation, itching, redness, edema, induration/infiltration, and other type of reaction; other type of reaction will be coded using MedDRA, same version as for AEs), if reaction at injection site, the severity (i.e., mild, moderate, or severe), and any action taken (i.e., no action, interruption of infusion, and other). The likely cause of the reaction will also be collected (i.e., insertion site,

drug, adhesive dressing, or other).

The frequencies and percentages of patients with local tolerability findings collected separately from AEs, will be summarized within treatment period and study visit. Description will be performed only on the Dasiglucagon group.

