10.2.3.2. Clinical Examinations

Vital Signs

Vital signs, including blood pressure, heart rate, respiratory rate, and SpO₂ will be measured according to the Schedule of Events (Section 17.1).

Twelve-lead Electrocardiogram

A standard 12-lead ECG will be performed while the child is in a sleeping or calm state according to the time points specified in the Schedule of Events (Section 17.1). If it is not practical or possible, then a 2-lead may be used.²¹ If arrhythmia is detected on a 2-lead ECG, this should be followed by a 12-lead ECG. All ECG recordings will be identified with the patient number, date, and time of the recording and will be attached to his or her medical record.

The ECG parameters (heart rate, PQ, QRS, QT, and QTcF) and any abnormality will be recorded and described in the eCRF, including the investigator's assessment of clinical significance (Abnormal, Clinically Significant; or Abnormal, or Not Clinically Significant). At subsequent visits, any clinically significant deterioration of a pre-existing condition, as well as any new clinically significant findings, will be recorded as AEs.

Echocardiogram

An echocardiogram will be performed according to the time points specified in the Schedule of Events (Section 17.1).

Physical Examination and Neurological Examination

A complete physical examination of body systems (excluding breast and genitourinary examinations) according to standard of care and a neurological examination (including cranial nerves, muscle strength and tone, reflexes, coordination, sensory function, and gait, all as applicable for the patient's age) will be performed according to the Schedule of Events (Section 17.1).

Local Tolerability

Local tolerability data will be collected separately from AEs. Within the eCRF, data will be collected on the nature of any reaction (erythema, pain, swelling, etc.), the severity (mild, moderate, or severe), and any action take (e.g., no action, interruption of infusion). The likely cause of the reaction will also be collected (e.g., insertion site, drug, or adhesive dressing).

Other skin findings will be collected along other AEs. If clinical suspicion of NME is made, data describing the lesion(s) will be collected as an AE of special interest (AESI) (see Section 11.1.8), together with a photograph or series of photographs of the lesion(s) uploaded to a central repository.

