12.4.4. Safety and Tolerability Analyses

Safety analyses will be conducted using data from the Safety Population (as defined in Section 12.3). Safety assessments will include the evaluation of AEs; clinical laboratory assessments (hematology, biochemistry, and ADAs); vital signs, physical examinations; ECGs, echocardiography, and local tolerability issues. No formal inferential analyses will be conducted for safety variables, unless otherwise noted.

Baseline is defined as the last non-missing assessment before first dose in each treatment period. All safety analyses will be summarized by treatment received within treatment period and by trial visit, if applicable.

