12.1.10.1. Adverse Device Effect

An adverse device effect (ADE) is an AE related to the use of an investigational medical device. This definition includes AEs resulting from insufficient or inadequate instructions for use, deployment, installation, operation, or any malfunction of the investigational medical device. This definition also includes any event resulting from use error or from intentional misuse of the investigational device.

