The trial sites will be supplied with the pumps and their components and will be asked to document receipt of this equipment. Each pump will be identified by a serial number that will be used for accountability and traceability; the device will be labelled "for investigational use only." The trial sites must store the devices in a secure area with restricted access and at the storage conditions indicated in the user manual ($+5^{\circ}C - 45^{\circ}C$). After a patient is enrolled into the trial, one (1) pump device will be allocated exclusively to this patient; disposables are not accounted for. Upon completion of the trial and if the patient is not continuing in the ZP4207-17106 trial, the pump must be returned to the site. The site will ship all returned pumps (with the exception of those continuing in 17106 trial) back to the sponsor upon completion of the trial.

The Roche pump is CE-marked and marketed in Germany, and it can administer very low doses. The pump is designed to deliver 0.05 to 25.0 units of U 100 insulin per hour in basal rates, which corresponds to 2 to 1000 µg dasiglucagon per hour. This dosing accuracy allows reliable dosing of dasiglucagon between 10 and 70 µg per hour in the clinical trial. Further, this pump has been used in pediatric diabetes treatment in the EU since 2010. However, the Accu-Chek Spirit Combo pump system will not be used within its approved indication. The pump will be used for the administration of the investigational glucagon analogue dasiglucagon for the indication of CHI. Additional compatibility testing and assessments were performed to ensure that the Accu-Check Spirit Combo pump system and its components are not adversely affected by using dasiglucagon instead of insulin. Also, testing was performed to ensure that dasiglucagon is stable and effective when administered via this pump system. The general management of the device, as well as the duration of contact of the pump material and infusion sets with human tissue, will be based on the approved intended use of the device. The complete infusion set will be changed every 2 days (48 hours) for the Accu-Chek Rapid-D link infusion set, and every 3 days (72 hours) as a maximum for the Accu-Chek FlexLink infusion set. Only the application and dosage of dasiglucagon via the Accu-Chek pump system requires an off-label change in practice

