9.1. Adverse Events

An AE is any untoward medical occurrence in a clinical trial patient administered a medicinal (investigational or non-investigational) product and which does not necessarily have a causal relationship with this treatment. An AE can therefore be any unfavorable and unintended sign (including an abnormal laboratory finding), symptom, or disease temporally associated with the use of a product, whether or not related to the product. Adverse events that begin after the first dose of dasiglucagon (dasiglucagon + SOC treatment group) or randomization (SOC only treatment group) will be defined as treatment emergent (TEAE).

The causal relationship of the AE to the study drug is determined by the investigator as Not Related, Unlikely, Possible, and Probable. These will be mapped to Unrelated (*Not Related* or *Unlikely*) and Related (*Possible* or *Probable*) for summarization purposes. Relationship for patients on SOC only is expected to be “Not related” according to data entry guidelines. If it is missing for a patient in this period it should be mapped to “Not related” other missing data will be mapped to “Related”.

Adverse event severity grades are reported as mild, moderate, or severe.

Each patient will be counted only once within each summation level system organ class (SOC) and preferred term (PT). If a patient experiences more than 1 TEAE within each summation level only, the TEAE with the strongest relationship or the maximum severity, as appropriate, will be

included in the summaries of relationship and severity. The summary will be presented in descending order of frequency of SOC and then PT within SOC based on dasiglucagon arm of period 1, then by standard of care only in period 1 and then by period 2.

The incidence of TEAEs will be summarized with frequencies and percentages for patients in Safety Set (including number of TEAEs occurring, as well as rate of events), by treatment group within treatment period and the following:

- SOC and PT
- SOC, PT, and severity
- SOC, PT, and relationship to study drug
- SAEs by SOC and PT

Rate of events will be described as Exposure-adjusted TEAE rate calculated by summing all events and dividing by total exposure time. For Standard of Care only the total exposure time will be calculated from randomization to day before first intake in treatment period 2.

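### Local tolerability is collected apart from AEs and described for dasiglucagon only, so the Period 1 by-arm TEAE tables may omit infusion-site reactions and understate the dasiglucagon excess

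*SAP*

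**What the plan says.** **Collection.** Protocol 10.2.3.2 states: "Local tolerability data will be collected separately from AEs". The form takes the nature of the reaction, its severity, the action taken (interrupting the infusion is one option) and the likely cause. The same section sends other skin findings to the AE record. SAP 9.7 repeats the separation and gives the visits: "Local tolerability data will be collected separately from AEs at Day 1 and Weeks 2, 4, 5, 6, and 9". It plans MedDRA coding only for reactions in the residual 'other' category.

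**Summary.** Under SAP 9.7, patients with local findings "will be summarized within treatment period and study visit". The next sentence narrows this: "Description will be performed only on the Dasiglucagon group".

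**General rule.** The protocol synopsis includes local tolerability among the safety data to be summarised by treatment, where applicable. Protocol 12.4.4 says: "All safety analyses will be summarized by treatment received within treatment period and by trial visit, if applicable". The opening of SAP section 9 has the same rule and adds a summary pooled over active treatment.

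**By-arm harm tables.** SAP 9.1 says: "The incidence of TEAEs will be summarized with frequencies and percentages for patients in Safety Set". These tables are by treatment group within period.

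**The concern.** The first secondary objective is the safety and tolerability of the subcutaneous infusion. Period 1 is the only randomised comparison that bears on it, because every patient receives dasiglucagon in Period 2. In Period 1 only the dasiglucagon arm has an infusion set. If infusion-site reactions sit on a separate form and do not reach the TEAE tables, a harm specific to one arm is missing from the one place where the arms are set side by side. A reader who takes the by-arm proportion with any TEAE as the overall tolerability comparison would then see too small a difference. The separate local tolerability table does not correct this, because it has one arm and is not combined with the TEAEs at patient level.

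**Working it through.** The plan states no rate of local reactions and no TEAE incidence, so there is no figure of its own to reproduce on this point. The check is a comparison of the texts, then an illustration of size.

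**1. Do local reactions reach the TEAE tables?**
- Towards no: the protocol and SAP both separate the two collections, and other skin findings are sent to AEs in contrast. The pre-listed reactions on the form (pain, itching, redness, edema, induration) have no planned MedDRA coding, so from that form they cannot enter a table by system organ class and preferred term.
- Towards yes: the AE definition in protocol 11.1.1 is broad, its list of things that are not AEs does not name local reactions, and protocol 11.2 requires every AE to be recorded.
- Result: a local reaction enters the TEAE tables only if the site also enters it as an AE. No text tells sites to do this, and none forbids it. Omission is the natural reading, but it is not a written rule.

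**2. Does the one-arm description fit the plan's general rule?**
The synopsis, protocol 12.4.4 and SAP section 9 all point to by-treatment summaries. Each carries a where-applicable or if-applicable qualifier; in the last two it follows the word for visit and reads most naturally as belonging to it. The one-arm sentence therefore departs from the general rule without flatly contradicting it.

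**3. How large could the gap be?**
Assume:
- q = incidence of any other TEAE, the same in both arms;
- l = risk, in the dasiglucagon arm only, of at least one reaction recorded solely on the local form, independent of other TEAEs;
- 16 patients per arm (32 randomised 1:1).

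The proportion with any TEAE or local reaction is q + l(1 − q) on dasiglucagon and q on standard of care. The TEAE tables show q in both arms. The hidden gap is

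q + l(1 − q) − q = l(1 − q).

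For example, with q = 0.5 and l = 0.3, the gap is 0.3 × 0.5 = 0.15, which is 15 points or 0.15 × 16 = 2.4 patients.

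| q | l = 10% | l = 30% | l = 60% |
|---|---|---|---|
| 30% | 7 points (1.1 of 16) | 21 (3.4) | 42 (6.7) |
| 50% | 5 (0.8) | 15 (2.4) | 30 (4.8) |
| 70% | 3 (0.5) | 9 (1.4) | 18 (2.9) |
| 90% | 1 (0.2) | 3 (0.5) | 6 (1.0) |

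If every local reaction is also entered as an AE, l = 0 and the gap is zero.

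**4. Is that range of l far-fetched?**
The German protocol (20.2.1.1) says: "The complete infusion set will be changed every 2 days (48 hours) for the Accu-Chek Rapid-D link infusion set". For the other set it gives 3 days as the maximum. Over 28 days this is 28/2 = 14 or 28/3 ≈ 9 insertions. With an assumed, undocumented reaction risk p per insertion, l = 1 − (1 − p)^n. For p from 1% to 5% this gives 9% to 37% with n = 9, and 13% to 51% with n = 14. This shows only that repeated insertion can turn a small risk per insertion into a sizeable risk per patient.

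**The case against.** The strongest reply has four parts.

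- **The omission is inferred.** Separate collection is not exclusion, and the AE definition and recording duty are broad enough to bring local reactions in. This stands. A reader might infer that the plan bars these reactions from the AE tables; it does not say so. What is missing is a statement either way.
- **The data are reported.** SAP 9.7 gives a Period 1 table for dasiglucagon, SAP 6.1.8 puts all collected data in listings, and serious reactions fall under the SAE rules. This stands too. The weakness is where the information sits, not that it is lost.
- **A standard-of-care column would be empty.** For infusion-site causes it is zero by design in Period 1. Its use is limited to other causes on the form, such as adhesive dressing, since both arms wear a CGM sensor. A reader might call it the only control for such reactions. The documents do not support that: nothing sends CGM-site reactions to this form, and other skin findings go to AEs. Nor does the unrestricted tick in the schedule of events prove collection in both arms, because dispensing of trial product is ticked at the same Period 1 visits without an arm limit.
- **Earlier experience suggests few reactions.** Protocol 5.3.3 and 5.3.6 report injection-site reactions as sporadic and of low frequency, and name nausea and vomiting as the most frequent related AEs. Calling local reactions the commonest expected harm would contradict this. Those trials were mostly short-term dosing, and 5.3.6 says that data on chronic administration are lacking, so they do not fix l for four weeks of infusion.

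A further tempting inference is that German and other sites will classify the same reaction differently. The German protocol says "An adverse device effect (ADE) is an AE related to the use of an investigational medical device" (12.1.10.1) and lists infusion-site pain, redness and swelling as anticipated device effects (20.3.2). But its section 11.2.3.2 also collects local tolerability apart from AEs. The ambiguity lies within that protocol, and a difference between countries is not shown.

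**Conclusion.** The point holds in a limited form. Local tolerability is described for one arm, on a form kept apart from AEs, and the documents do not say whether a local reaction is also an AE. On the natural reading, the Period 1 by-arm TEAE tables can omit infusion-site reactions, and the proportion with any TEAE may understate the dasiglucagon excess.

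The size cannot be derived from the documents. Under equal other-TEAE incidence in the two arms, independence, and no infusion-site reactions on standard of care, the gap is l(1 − q). It is small where nearly every child has another TEAE and larger where about half do, as the table shows. Safety is descriptive, so no test, error rate or efficacy result is affected. The correction is worth making because it concerns the only randomised view of a stated objective and costs little.

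**What to change.** 1. **SAP 9.7.** Replace the one-arm sentence. Summarise local tolerability by treatment group in Period 1 (patients with any finding, and by recorded cause), showing standard-of-care findings where they were collected, and for dasiglucagon in Period 2. If the form was not completed for standard-of-care patients, say so in a footnote so that a blank is not read as an observed zero.
2. **SAP 9.1.** Leave the TEAE tables unchanged. Add one supplementary Period 1 by-arm row: patients with any TEAE or local tolerability finding, each patient counted once. Do not add event counts or rates unless the form supports them; the fields described include no onset date, event count or link to an AE record.
3. **State the boundary.** Say whether local reactions are also entered as AEs.
4. **SAP section 10.** Record the change to the local tolerability display.

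The cost is SAP wording, one extra table column and one table row, from data already scheduled for collection. The reported tolerability of dasiglucagon may look slightly less favourable. No protocol amendment, extra visit or extra patient is needed.

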9.8. Concomitant Medication

Concomitant medications will be coded using World Health Organization Drug Dictionary Enhanced (WHO-DDE) (Version September 01, 2018 or later) thesaurus.

Medications that started before first dose of dasiglucagon (dasiglucagon + SOC treatment group) or randomization (SOC only treatment group) will be considered prior medications if they were stopped before first dose of dasiglucagon/randomization. Any medications ongoing at start of trial will be considered to be concomitant medication ongoing at start. If a medication starts during the trial it will be considered as medication starting during the trial.

Concomitant Medication are described on the FAS according to randomized treatment.

Frequencies and percentages will be summarized descriptively by Anatomical Therapeutic Chemical (ATC) classification Level 4 and Preferred Name, if applicable, by overall patients and treatment group within treatment period. The summary will be presented in descending order of frequency of ATC and then Preferred Name within ATC based on overall patients.

10. Changes from Planned Analysis

- The protocol mentioned how to handle analyses involving trial site; however, since randomization is stratified by region (US vs non-US), region will be included in the analyses (it is not included in the protocol). Thus no analyses will be performed by trial site.
- The Full Analysis Set definition was clarified to indicate that the primary endpoint baseline assessment needs to be non-missing for a patient to be included in the set.
- A PK Set was added to support summaries of PK data.
- In the protocol a common methodology for the imputation of missing data for primary and key secondary endpoints was described. This has been split into appropriate methods for imputing missing event data based on the negative binomial model and non-event data based on the MCMC method for non-monotone missing data and sequential regression for monotone missing data.
- Baseline for endpoints related to external CGM data will be defined taking into account data from 14 days before randomization, those days will not necessary be consecutive, this is different from baseline definition of the other endpoints.

11.1. Pharmacokinetic Analysis

Plasma concentrations are collected on week 6 and week 9 as per Schedule of Events [Table 2](#). Descriptive summaries will be presented for plasma PK concentrations by study visit and infusion rate (in $\mu\text{g}/\text{kg}/\text{hr}$) at the end of Treatment Period 2, as described in Section [7.4](#). Information pertaining to PK data collection will be listed.

PK analysis is performed using PK population according to actual treatment received.

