9.7. Selection of Doses in the Trial

Both the starting dose and the maximum allowed doses are based on experience with marketed glucagon products in this patient population.¹¹

At present, no pediatric PK data are available for dasiglucagon. However, an approximate estimation of expected drug concentration in a 3 kg patient has been made by extrapolation of a previously made PK model for pediatric patients with weights between 25 and 45 kg. 15

The predicted plasma concentration is expected to give a low PD response at the lowest dose level and be above maximum effect at the highest dose level. The maximum expected plasma concentrations of dasiglucagon is in the range of what is achieved following a rescue dose to adults. The doses of dasiglucagon will be titrated to meet the needs of the individual patient. The titration will stop when no additional PD effects are observed as the infusion rate is increased. The infusion rate of dasiglucagon will be monitored and adjusted to meet the needs of the individual patient throughout the trial period.

Since the dasiglucagon dose is titrated individually based on the desired PD response, it does not need to be related to any measure of the patient's size.

The titration interval of 2 hours was chosen based on the PK data of dasiglucagon showing that an approximate steady-state is expected after 2 hours.

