9.10. Treatment Compliance

Compliance data will be collected. Infusion details will be recorded in the patient's eCRF by trial personnel and drug accountability will be performed as detailed in the pharmacy manual.

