If subject discontinues trial before reaching Week 9:			
Week 2	Days 8 – 14	Date 1 date + 7 days	Earliest of Analysis Start Date + 6 days, or date of trial discontinuation
Week 3	Day 15 – 21	Date 1 date + 14 days	Earliest of Analysis Start Date + 6 days, or date of trial discontinuation
Week 4	Days 22 – 28	Date 1 date + 21 days	Earliest of Analysis Start Date + 6 days, or date of trial discontinuation
Weeks 2-4	Days 8 – 28	Same as Week 2 Analysis Start Date	Same as latest of Week 2, Week 3, or Week 4 Analysis Stop Date
Week 5	Days 29 – 35	Week 5 date	Earliest of Analysis Start Date + 6 days, or date of trial discontinuation
Week 6	Days 36 – 42	Week 5 date + 7 days	Earliest of Analysis Start Date + 6 days, or date of trial discontinuation

Study Week	Planned Days	Analysis Start Date	Analysis Stop Date
Week 7	Days 43 – 49	Week 5 date + 14 days	Earliest of Analysis Start Date + 6 days, or date of trial discontinuation
Week 8	Days 50 – 56	Week 5 date + 21 days	Earliest of Analysis Start Date + 6 days, or date of trial discontinuation
Weeks 6-8	Days 36 – 56	Same as Week 6 Analysis Start Date	Same as latest of Week 6, Week 7, or Week 8 Analysis Stop Date

- **Study Visit** = in-clinic visit as per the schedule of events, to be used for assessments that can only occur during a clinic visits (e.g., PedsQL, safety assessments like clinical laboratory assessments and vital signs).
- **Change from baseline** = value at current time point – value at baseline.
- **TEAE** = an AE with an onset at the time of or following the start of treatment with the trial drug (dasiglucagon + SOC arm) or date/time of randomization (SOC only arm) through the Follow-up visit or Early Termination visit, whichever occurs first.
- **PK Clearance:**

$$CL/f \text{ (L/h)} = R_0/C_{ss}$$

where R_0 = infusion rate (pmol/h) and C_{ss} = concentration at steady state (pmol/L), weight ($1\mu\text{g/kg/hr} = 295.7 \text{ nmol/kg/h}$)

- **SMPG-detected Hypoglycemia episode** = PG <70 mg/dL or 3.9 mmol/L, as detected by SMPG and reported in the eCRF. A single hypoglycemia episode is defined as up until 60 minutes from the start of the episode even if normoglycemia (>70 mg/dL) is not reached within this time. A new episode of hypoglycemia is to be reported when the next PG value below 70 mg/dL (3.9 mmol/L) is measured. Episodes are defined as the ones entered in the eCRF, no statistical programming will be done to define an episode.

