7.4. Exposure and Compliance

Study drug administration will be summarized separately for total dasiglucagon exposure ($\mu\text{g}/\text{kg}$) and total duration of exposure (days), respectively, for each treatment period. The total dasiglucagon exposure will also be described by study week. Additionally, the infusion rate, defined as the average hourly weight-adjusted infusion rate over the last 7 days of the respective treatment period (i.e., $\mu\text{g}/\text{kg}/\text{hr}$ and $\mu\text{g}/\text{hr}$), will be summarized for each treatment period and each study week.

8. Efficacy Analysis

The FAS and PP Set will be used to summarize efficacy data. The PP Set will be used only as supportive analysis. Patients will be analyzed by treatment period according to the planned treatment group (SOC and dasiglucagon + SOC for Treatment Period 1 and dasiglucagon + SOC for Treatment Period 2).

The efficacy analysis will be separated into 3 categories:

1. Treatment Period 1, FAS
2. Treatment Period 1, PP (primary and key secondary endpoints only)
3. Treatment Period 2, FAS

Efficacy Procedures

Plasma Glucose Monitoring: During the study, SMPG assessments will be performed regularly (at least 3 times daily, preferably before meals) to evaluate efficacy. At each visit, the investigator will check for patient compliance in number of daily SMPG measurements and that hypoglycemia episodes are recorded in the diary.

Continuous Glucose Monitoring: CGM will be used in a blinded manner to evaluate efficacy in terms of hypoglycemia episodes. The CGM is required for the 2 weeks up to randomization, during Week 2-4 of Treatment Period 1, and during Week 6-8 of Treatment Period 2. However, short pauses of 1-3 days due to skin irritation or discomfort are allowed after consultation with the investigator.

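### SAP 11.1 sets the Week 6 dasiglucagon concentrations against an infusion rate delivered 14 to 20 days after the sample

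*SAP*

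**What the plan says.** Dasiglucagon levels are measured twice, both times in Treatment Period 2: "Plasma concentrations are collected on week 6 and week 9 as per Schedule of Events" (SAP 11.1). The schedule of events puts these at Visit 6 (Day 36) and Visit 7 (Day 57), each with a window of 2 days either way. SAP 2.2.3 and Protocol 10.2.2 describe them as steady-state levels.

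For the analysis, SAP 11.1 states: "Descriptive summaries will be presented for plasma PK concentrations by study visit and infusion rate". The unit is µg/kg/hr, and the sentence fixes which rate is meant with the words "at the end of Treatment Period 2, as described in Section"; the section it cites is 7.4. SAP 7.4 gives the infusion rate as "defined as the average hourly weight-adjusted infusion rate over the last 7 days of the respective treatment period", and adds that it will be summarised for each treatment period and each study week.

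SAP 6.1.7 lists a clearance formula, CL/f = R0/Css, where R0 is an infusion rate and Css the steady-state concentration. It gives no time reference for R0.

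On dosing, Protocol 9.7 (10.7 in the German version) says: "The infusion rate of dasiglucagon will be monitored and adjusted to meet the needs of the individual patient throughout the trial period". For the titration interval it says that "an approximate steady-state is expected after 2 hours". On records, Protocol 9.10 says: "Infusion details will be recorded in the patient's eCRF by trial personnel".

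**The concern.** If steady state is approached in about 2 hours, a concentration reflects the rate of the preceding hours. It cannot reflect a rate set two or more weeks later. Yet SAP 11.1 names a single rate, from the end of the period, for samples at both visits, and no other section assigns a visit-matched rate to the Week 6 sample. A child whose rate went up or down after Day 36 would appear in the Week 6 summary at a dose that did not produce the level shown.

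What is at stake is the Week 6 half of the planned dose-exposure description. Protocol 9.7 says that no pediatric pharmacokinetic data are available for dasiglucagon, and these two samples are the only drug-level measurements planned. The Week 6 sample is also the earlier one on treatment. Children who received SOC alone in Treatment Period 1 (about 16 of 32 under 1:1 allocation) are then about 7 days past initiation (Day 29 to Day 36).

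**Working it through.** **Inputs**
- Week 6 sample: Day 36, window ±2 days (schedule of events, Visit 6).
- Week 9 sample: Day 57, window ±2 days (schedule of events, Visit 7).
- Study-week rule (SAP 6.1.7): Week 8 stops at the Week 9 visit date minus 1 day and starts 6 days before that stop.
- Time to approximate steady state: about 2 hours (Protocol 9.7).

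**1. Reproduce the SAP's own window.** Stop = 57 − 1 = Day 56. Start = 56 − 6 = Day 50. This matches the planned Days 50-56 that SAP 6.1.7 gives for Week 8, which are the last 7 days of Treatment Period 2.

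**2. Gap for the Week 6 sample, nominal days.** The first window day is 50 − 36 = 14 days after the sample and the last is 56 − 36 = 20 days after. The midpoint is 53 − 36 = 17 days after. The whole window lies after the blood draw.

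**3. Gap for the Week 6 sample with visit windows.**
- Smallest: sample on Day 38 and Week 9 visit on Day 55. The window is Days 48-54, and 48 − 38 = 10 days.
- Largest: sample on Day 34 and Week 9 visit on Day 59. The window is Days 52-58, and 58 − 34 = 24 days.

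**4. Gap for the Week 9 sample.** 57 − 56 = 1 day and 57 − 50 = 7 days, both before the sample. The direction is right and the lag is short.

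**5. An alternative close to hand.** Study Week 5 is planned as Days 29-35, so it precedes the Day 36 sample by 1 to 7 days. That is the same lag that the current rule gives the Week 9 sample. For children starting dasiglucagon in Treatment Period 2, Week 5 includes the initial titration.

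**6. Size when the rate changes.** The rate assigned to the Week 6 sample differs from the rate at sampling by the factor (mean rate over Days 50-56) / (rate at Day 36). The changes below are assumed, each one 10 µg/hr step within the permitted 10-70 µg/hr:

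| Rate at Day 36 (µg/hr) | Mean rate, Days 50-56 (µg/hr) | Factor |
|---|---|---|
| 10 | 20 | 2.00 |
| 30 | 40 | 1.33 |
| 60 | 70 | 1.17 |
| 70 | 60 | 0.86 |
| 20 | 10 | 0.50 |
| any | unchanged | 1.00 |

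A Week 6 CL/f computed with the end-of-period rate as R0 would be off by the same factor. These figures illustrate the mechanism. They are not estimates, because the documents give no frequency or size of rate changes after Day 36.

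**The case against.** The strongest reply is that the sentence in 11.1 can be read as two separate summaries: concentrations by visit, and the end-of-period infusion rate on its own. The SAP gives no rate categories, and a rate in µg/kg/hr is continuous, so using it as a grouping variable is not workable as written. On that reading no Week 6 level is set against a later dose. This is a fair point about the wording, but it leaves the Week 6 concentration with no rate at all, and the same clarification is needed.

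Second, a reader might infer that the plan will produce biased Week 6 clearances. The documents do not support that. SAP 11.1 plans no CL/f summary, and 6.1.7 does not link R0 to the 7.4 average. Its R0 is in pmol/h, whereas 7.4 works in µg/kg/hr and µg/hr. What stands is only that R0 has no stated time.

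Third, a reader might infer that both visits are affected, or that 7.4 cannot yield weekly rates. The Week 9 pairing is reasonable. The natural meaning of a rate summarised for each study week is that week's average, although the definition in the same sentence does not say so.

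Fourth, titration moves in 2-hour steps during a short hospital stay, so rates may have settled by Day 36. That is possible. The protocol allows later adjustment, and nothing in the documents settles how often it happens.

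Fifth, pharmacokinetics is neither a stated objective nor among the tested hypotheses. SAP 6.1.8 lists all collected data, so the pairing could be redone later. This limits the importance of the point but does not make the written rule correct.

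**Conclusion.** The point holds for the Week 6 sample. On the plain reading of SAP 11.1 with 7.4, the Day 36 concentration is summarised by a rate delivered 14-20 days later (10-24 days with visit windows). The protocol's own 2-hour steady-state expectation makes that the wrong rate for any child whose infusion changed in between. This is a stated rule that mis-pairs dose and level, and not merely a missing detail.

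The consequence is confined to descriptive pharmacokinetics. No primary or key secondary inference is touched, and the error is zero for a child whose rate stayed the same. The conclusion rests on the plain parse of 11.1, on planned visit days, and on at least some rates changing after Day 36, which the protocol permits but does not quantify. It would go too far to call the Week 6 exposure data wrong overall, or to attach a percentage error to them.

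**What to change.** - **SAP 11.1:** summarise each concentration against the infusion rate (µg/kg/hr) in force when that sample was drawn, taken from the eCRF infusion records. If that is not recorded, use the average over the study week just before the sample: Week 5 for the Week 6 sample, with a note that it includes titration in children who began on SOC alone, and Week 8 for the Week 9 sample. Use the body weight nearest the sample. Weight is not scheduled at Visit 6, so for the Week 6 sample this will normally be the Visit 5 weight.
- **SAP 6.1.7:** state that, if CL/f is calculated, R0 is the rate at the time of the matching Css.
- **SAP 7.4:** define the weekly rate as the average over that study week, and keep the last-7-days average for the treatment-period summary.
- **Sample handling:** flag samples with a recorded rate change or interruption in the preceding 2 hours. Do not exclude them automatically.

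The cost is SAP wording and programming, with no new data collection. One limit applies: Protocol 9.10 confirms that infusion details are recorded but not that rate changes at home are time-stamped. The study-week fallback is there for that reason, and the 2-hour flag can be applied only where times exist.
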